14.3. Institutional Review Board

The investigational site will obtain the written and dated approval/favorable opinion of the IRB for the clinical investigation inclusive of an approved informed consent document before recruiting subjects and implementing all subsequent amendments, if required.

A copy of the IRB approval and ICF must be received by DCRI before recruitment of subjects into the study.

Any amendment to the protocol will require review and approval by the IRB before the changes are implemented to the study. All changes to the ICF must be IRB approved; a determination will be made regarding whether a new ICF needs to be obtained from participants who provided consent, using a previously approved ICF.

Annual IRB approval and renewals will be obtained throughout the duration of the study as required by applicable local/country laws or regulations or IRB requirements. Copies of the study reports and the IRB continuance of approval must be provided to DCRI.

14.4. Sponsor Responsibilities

All information and data sent to DCRI concerning subjects or their participation in this study will be considered confidential by DCRI and will be kept confidential in accordance with all applicable laws and regulations. Only authorized DCRI personnel and/or a NIST representative, the applicable CIED lead manufacturer's representatives, and AAMI will have access to this information. Authorized regulatory personnel have the right to inspect and copy all records pertinent to this study. Study data collected during this study may be used by AAMI for the purposes of this study, publication, and to support future standards. All data used in the analysis and reporting of this study or shared with a third-party researcher will be without identifiable reference to specific subjects.

15. Monitoring

All data is collected at the time of enrollment and imaging; therefore, no on-site monitoring is planned.

16. Potential Risks and Benefits

16.1. Anticipated Adverse Events

The following potential adverse events (AE) have been identified for the study related to the imaging procedure and requirements. This study will not report adverse events associated with the pulse generator or lead implant procedure as subjects will already be implanted. Adverse events associated with the pulse generator will not be collected as a part of this trial as the imaging procedure will not affect the device. **Table 7** indicates potential adverse events related to participation in this study.

Table 7: Potential Adverse Events

Potential Adverse Events
Adverse or allergic reaction to adhesive from ECG tabs (i.e. rash, redness etc.)
Pain or discomfort from required shoulder movement
Dislodgement of the lead (RA/LV/RV)
Adverse reaction to the imaging procedure radiation (See section 16.2.1)

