4.3.3. Perform 3-D reconstruction of Lead Trajectories

For each subject, cine fluoroscopy data (DICOM file) for the RV pacing or defibrillator lead will be reconstructed to generate 3D trajectories in time and spacing in accordance with the method described in AAMI_PC_WG1_N726 Methodology for 3-D Reconstruction of Lead Trajectories from Bi-Plane Fluoroscopy DICOMs. An example of a 3-D lead trajectory is shown in Figure 5.

For each lead, the maximum cyclic curvature, ΔC_{max} , and the corresponding value of lead stiffness will be determined by the lead manufacturer, for each region (intracardiac region, extravenous region, and connector region).

5. Device Description

The devices in this study are FDA approved, commercially available, Pacemaker (PM) systems and implantable cardioverter defibrillator (ICD) systems.

Pacemaker systems are composed of any approved, commercially available dual chamber or single chamber pacemaker and at least one implantable pacing lead implanted in the right ventricle. The pacing leads included in this study are listed in Table 1.

Table 1: RV Pacing Leads

Manufacturer	Model(s)	Description
Biotronik	Siello S, Solia S	Active Fixation Leads
Boston Scientific	4452, 4453, 4456, 4457	FINELINE II/FINELINE II Sterox Passive Fixation (polyurethane)
Boston Scientific	4463, 4464, 4465, 4469, 4470, 4471	FINELINE II/FINELINE II Sterox EZ Positive Fixation (polyurethane)

ICD systems are composed of any approved, commercially available dual chamber or single chamber ICD and at least one implantable defibrillation lead implanted in the right ventricle. The defibrillation leads included in this study are listed in Table 2.

Table 2: Defibrillation Leads

Manufacturer	Model(s)	Description
Abbott	LDA 210Q	Optisure Single Coil Defibrillation Lead
	LDA 220Q	Optisure Dual Coil Defibrillation Lead
	LDA 230Q	Optisure Dual Coil Defibrillation Lead
Medtronic	6935M	Quattro Secure Single Coil Defibrillation Lead

6. Required Imaging System

Center selection criteria include access to a biplane fluoroscopy system with capability of at least 15 frames per second (fps) and image portability using removable media or secure network. The following equipment must be available at each study site to support study activities;

- Biplane fluoroscopy system with:
 - capability of fluoroscopy (scout image) capture at 7.5 fps or less **and** Cine recording at 15 fps or more
 - capability of image recording in a DICOM format

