Note: If the PG is implanted on the left, the left arm will be in motion; if implanted on the right, the right arm will be in motion.

1. Subjects will be asked to assume a supine position in the biplane system field of view, and coached to perform a movement at a starting point with the arm on the table alongside the body (Figure 11A) to follow a course along the long axis of the body as high as possible (Figure 11B).
2. Short taps of fluoroscopy will be used to optimize adequate visualization of the suture-sleeve and connector regions of the defibrillator/pacing lead in the center of the imaging plane of both Image Intensifiers during this arm movement. Image Intensifiers shall be at an angle of $90^\circ \pm 45^\circ$ to each other. Lowest intensity exposure at 7.5 frames/ second or less will be used for this purpose. (Approximately 4 seconds each) Note: It is required that for each image sequence the PG and entire extracardiac region (including the venous access site) must be visible throughout the entire image sequence.
3. A cine- fluoroscopy exposure capture (15 frames/second or more) of the defibrillator/pacing lead will be acquired during the arm along body movement. (3 seconds)
4. Have the subject leave the imaging field without moving the x-ray cameras.
5. A calibration object will be placed in the field of view, and adjusted without moving the x-ray camera, until a minimum of 12 markers are visible in both views.
6. The calibration object will be imaged without moving the biplane system (approximately 1 second)

[figure not shown]
Image Sequence 3:**Shoulder movement-2 (Cross-chest movement) Imaging Protocol**

1. Note: If the PG is implanted on the left, the left arm will be in motion; if implanted on the right, the right arm will be in motion. Subjects will be asked to assume a supine position in the biplane system field of view, and coached to perform a movement at a starting point with the arm on the table alongside the body (Figure 11A) to follow a course across the chest (Figure 11C).

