17.1. Reportable Events by investigational site to DCRI

The investigator will be required to assess and classify each AE that occurs during the time of the imaging procedure. AEs that occur following consent, but prior to the imaging procedure will not be collected.

Events collected during this study will include adverse events, serious adverse events and unanticipated adverse events (inclusive of serious) **specific to the imaging procedure duration**. When possible, the medical diagnosis should be reported as the event term, not individual symptoms. Adverse events must be recorded in the eCRF. Underlying diseases are not reported as an adverse event.

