17.2. Definitions

17.2.1. Adverse Event Definitions

An adverse event (AE) is defined as any untoward medical occurrence, unintended disease or injury, or untoward clinical signs (including abnormal laboratory findings) in subjects that occurs during the course of the study (defined as occurring during the imaging procedure), whether or not directly related to the imaging procedure.

Adverse Events are classified as a serious adverse event (SAE) as defined by *MEDDEV 2.7/3* if one or more of the following consequences are fulfilled:

- led to death
- led to serious deterioration in the health of the subject as defined by either:
 - a life-threatening illness or injury or
 - a permanent impairment of a body structure or function or
 - in-patient hospitalization (>24 hours) or prolongation of existing hospitalization or
 - a medical or surgical intervention to prevent life-threatening illness or injury or permanent impairment to a body structure or function
- led to fetal distress, fetal death, or a congenital abnormality or birth defect

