17.5. Investigator Reporting Requirements

The requirements for investigators to report relevant adverse events (see section 16.1) to DCRI are as shown in Table 9.

Table 9: Communication requirements for reporting to DCRI

Event Classification	Communication Method	Communication Timeline
Serious Adverse Event	Complete AE eCRF page with all available new and updated information.	Within 3 calendar days of first becoming aware of the event or as per local/regional regulations. Reporting required through the end of the study participation
	Provide all relevant source documentation (de-identified/pseudonymized) for reported event.	At request of DCRI
Adverse Event	Complete AE eCRF page, which contains such information as date of AE, treatment of AE resolution, assessment of seriousness and relationship to the device. Provide all relevant source documentation (de-identified/pseudonymized) for reported event.	In a timely manner (e.g. Recommend within 10 business days) after becoming aware of the information Reporting required through the end of the study subject participation.

The requirements for investigators to report other information to DCRI are as shown in Table 10.

Table 10: Additional Investigator Reporting Responsibilities

Type of Report	Report to DCRI	Report to IRB	Time Constraints of Notification
Subject Withdrawal	Required	As Required	Within 5 working days after notification of the event
Withdrawal of IRB Approval	Required	N/A	Within 5 working days of receipt of notice of withdrawal of approval
Progress Report	Required	Required	At, minimum annually

Significant Deviations from Investigational Plan	Required	Required	Within 5 working days after emergency to protect life or physical well-being of subject, otherwise prior approval by DCRI is required
Informed Consent Not Obtained	Required	Required	Within 5 working days of occurrence

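### Section 16.1 excludes pulse-generator adverse events that Sections 17.1 and 17.2.1 bring into scope, so a shock or pacing loss during the arm movements may go unrecorded when no lead dislodgement is diagnosed

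*Combined protocol and SAP*

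**What the plan says.** Section 16.1 makes two exclusions. The first removes events of the original generator or lead implant procedure, because subjects already carry the system. The second removes a class of event: "Adverse events associated with the pulse generator will not be collected as a part of this trial as the imaging procedure will not affect", its object being the device. Table 7, in the same section, lists among the potential events of participation "Dislodgement of the lead (RA/LV/RV").

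Other sections set a wider scope:

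- Section 17.1: "Events collected during this study will include adverse events, serious adverse events and unanticipated adverse events (inclusive of serious"), limited to the duration of the imaging procedure. It adds: "When possible, the medical diagnosis should be reported as the event term, not individual symptoms".
- Section 17.2.1 counts an untoward occurrence during imaging as an adverse event "whether or not directly related to the imaging procedure".
- Section 14.2 has the investigator report all adverse events to DCRI, as the protocol requires, and assess each for seriousness and relationship to the procedure.
- Section 17.3 and Table 8 grade relationship to the study procedure. Table 9 in Section 17.5 describes the AE form as containing "assessment of seriousness and relationship to the device".
- Section 17.5 introduces its reporting requirements by pointing to 16.1 for the relevant events.

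Section 5 describes what is implanted: "ICD systems are composed of any approved, commercially available dual chamber or single chamber ICD and at least one implantable defibrillation lead" in the right ventricle, with a parallel description for pacemaker systems.

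**The concern.** The second exclusion in 16.1 settles relatedness for a whole class of event by assumption. Everywhere else the protocol leaves that judgement to the investigator, event by event, on the Table 8 scale. Because 17.5 points to 16.1, the exclusion is not background text: a site deciding whether to complete an AE form is sent to it.

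The arm movements are the part of the session that loads the lead between generator and vein. If a subject has a shock or loses pacing or sensing during them, and nobody has diagnosed a dislodgement, the site has two instructions that point in opposite directions. One site may record the event and another may not. At stake is whether the safety record can be relied on for this type of event. Section 16.2 calls the study minimal risk, and an absence of recorded generator events would not support that statement if sites were told not to record them.

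**Working it through.** No sample size, rate or test is involved, so the check is a comparison of the sections.

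**Step 1. Does the exclusion add anything to the implant-procedure exclusion?** Yes. The sentence before it already removes events of the implant procedure. This one must therefore remove something further, namely events of the generator itself, including events during imaging.

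**Step 2. Is the stated reason consistent with the rest of the protocol?** Only if *device* means the generator alone. Section 5 uses the word for systems of generator plus lead. On that meaning, Table 7 lists an effect on the device as a potential event of participation.

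**Step 3. What happens to each kind of event during an arm movement?**

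| Event | 17.1 and 17.2.1 | 16.1 | Result |
|---|---|---|---|
| Dislodgement diagnosed | In scope | Listed in Table 7 | Reportable |
| Shock or loss of pacing or sensing, traced to a diagnosed dislodgement | In scope, under the diagnosis | Covered by the Table 7 entry | Reportable as dislodgement |
| Shock or loss of pacing or sensing, no dislodgement diagnosed | In scope | Can be read as generator-associated | May be omitted |

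Only the third row is in conflict. The diagnosis rule in 17.1 resolves the second row but not the third, because it applies only when a diagnosis is possible.

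**Step 4. Does Section 17.4 resolve the third row?** No. It asks for events, during or after imaging, that the investigator classifies as related to the procedure. An event that 16.1 has already taken out of collection may never reach that classification.

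**Step 5. Is the form consistent?** Table 9 refers to relationship to the device, while 14.2, 17.3 and Table 8 refer to relationship to the procedure. This mismatch does not itself lose events. It does leave a site unsure which relationship to record, in the same area where 16.1 says the device is unaffected.

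**Step 6. How far does it reach?** To every enrolled subject (80 to 120 under Section 8.2) and to both arm-movement sequences in 11.1.1. The documents give no expected rate of dislodgement, shock or pacing loss, so the number of events affected cannot be calculated.

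**The case against.** The best defence is that the exclusion names the pulse generator and not the lead. In that sentence *device* most naturally refers back to the generator, and the protocol elsewhere lists generator and lead details separately. Dislodgement is expressly in Table 7, its signs would be reported under the diagnosis, and 17.4 picks up later events judged related. Section 17.2.1 is a definition, and other sections may properly narrow what is collected. Most of this stands. It removes the first two rows of the table and softens the point about Section 5. It does not remove the third row.

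A reader might infer more than the documents support:

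- *That dislodgements or their signs go uncounted.* They do not once diagnosed. Nor do the documents say that shock or failed pacing or sensing are the likeliest signs of dislodgement.
- *That connector events are excluded by rule.* The endpoint sections treat the connector as a region of the lead, so such an event is not plainly a generator event.
- *That the order of imaging is part of this fault.* The intracardiac cine comes first, and for each arm movement the protocol requires that "the PG and entire extracardiac region (including the venous access site) must be visible throughout the entire image sequence". That bears on whether a dislodgement would be seen. Changing 16.1 leaves it as it is.
- *That a confidence bound on an event rate is lost.* No safety rate or bound is planned, so no planned analysis changes.

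There is also a separate reporting-window question. Section 17.4 asks for related events after imaging, but Table 9 ends reporting with participation, which 8.2 ends at image acquisition. It should be handled on its own.

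**Conclusion.** The point holds as a narrow conflict between stated rules. Section 16.1 excludes generator-associated events, and 17.5 makes 16.1 the reference for what is relevant. Sections 17.1, 17.2.1 and 14.2 bring the same events into scope when they occur during imaging. The practical consequence is limited to a shock or a loss of pacing or sensing during the session with no dislodgement diagnosed, which may be left out of the safety record. How often that would happen cannot be stated.

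The conclusion assumes that a site could reasonably class such an event as associated with the generator. The protocol does not say that it must, so it would be too strong to say that these events are certain to be lost. It would also be too strong to say that the study could never contradict its minimal-risk statement, since dislodgement, pain, radiation reactions and serious events remain reportable. The primary endpoints are unaffected. The correction is still worth making, because it changes which safety events are recorded and costs little.

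**What to change.** 1. In 16.1, delete the sentence that excludes pulse-generator adverse events. Keep the exclusion of events from the original generator or lead implant procedure.
2. In its place, state that any generator- or lead-associated event within the AE reporting period, for example a shock or a loss of pacing or sensing, is recorded on the existing AE eCRF and classified with the Table 8 procedure-relatedness scale.
3. In Table 9, replace relationship to the device with relationship to the procedure, or collect both, and check that the eCRF field matches.

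The cost is one sentence deleted, one added and one phrase aligned, with the IRB review that 14.3 requires for any amendment. The downside is a few extra AE forms. No visit, image or test is added. The change governs what is recorded once an event is noticed and does not improve detection of an unseen dislodgement.

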16.2. Risks Associated with Participation in the Clinical Study

This study involves minimal risk to subjects. Including by not limited to fluoroscopy/radiation exposure. It is estimated that it will take approximately 10 minutes of time to optimally position cameras and acquire images. See specifics below. The risk is considered very low and clinically acceptable.

16.2.1. Radiation Exposure

All study participants will receive standard biplane fluoroscopy x-radiation. X-ray exposure has been shown to increase the risk of cancer, as well as excessive radiation exposure can cause skin injury, the severity of which depends on dose to skin and ranges from hair loss, to skin irritation, to severe skin burns. However, the incremental amount of x-ray used in this study is expected to be minimal and is not expected to have significant, if any clinical consequence for the subject.

In a standard x-ray exposure (2D fluoroscopy), the x-ray tube is stationary. This directs the x-radiation to a limited area of skin as it enters the body, reducing the potential risk of adverse effects.

Radiation exposure can be quantified as "absorbed dose to skin", in units of Gray (Gy). The National Council on Radiation Protection & Measurement¹⁶ provides guidance for 2D exposure that can cause injury. A dose of <2000 mGy is considered insignificant or very low. A dose of 2000 mGy can cause early transient erythema (reddening of the skin).¹⁷

A previous lead imaging study performed in the same manner as the study imaging procedure in section 11.1.1 showed the absorbed dose to skin, as < 300 mGy (range 45-287) for an exposure time \leq 45 seconds (range 22-45).¹⁸ This exposure time is the same as what is expected for the HUCS study subjects.

To put this dose of radiation into perspective, the following comparisons are provided:

1. The absorbed dose to skin for a diagnostic coronary angiography procedure has been reported as 1350 mGy (range 900-1910).¹⁹
2. The absorbed dose to skin for a percutaneous transluminal coronary angioplasty (PTCA) is 3760 mGy (range 2400 - 5560).²⁰

The radiation exposure is not expected to have any acute adverse effects or any discernable effects from the low level of exposure. However, it is possible that following the fluoroscopic procedure, the skin area exposed to the x-rays could react to produce an effect similar to a sun burn.

16.3. Risk Minimization

To minimize radiation exposure the principal investigator will train other investigators/site staff on optimal techniques to acquire images. Only short taps of fluoroscopy will be utilized for scout images.

To minimize procedural time on the table, laboratory staff will be trained on optimal setup procedures.

These procedures will be done in a clinical or hospital setting. If unforeseen issues arise during the procedures (i.e. subject becomes unstable or experiences a medical emergency), medical personnel will be available.

¹⁶ NCRP Report No. 168, Radiation Dose Management for Fluoroscopically-Guided Interventional Medical Procedures, Table 2.5, National Council on Radiation Protection and Measurements, [name]

¹⁷ NCRP Report No. 168, Radiation Dose Management for Fluoroscopically-Guided Interventional Medical Procedures, Table 2.5, National Council on Radiation Protection and Measurements, [name]

¹⁸ Internal Medtronic Data (Unpublished)

¹⁹ Mahesh, M. (2001). Fluoroscopy: patient radiation exposure issues. Radiographics, 21(4), 1033-1045

²⁰ Mahesh, M. (2001). Fluoroscopy: patient radiation exposure issues. Radiographics, 21(4), 1033-1045

16.4. Anticipated Benefits

There are no benefits to study subjects participating in the study. The study results could benefit future patients who receive defibrillator or pacing leads by improving on current test methods and future lead designs.

No data exists in regard to the use conditions experienced by implanted leads in the human population. Defibrillation and Pacing leads are life-saving and life-sustaining devices that have to withstand the rigors of the human environment to function adequately. The gap in this knowledge-base has resulted in multiple large-scale recalls with currently existing test methods being unable to predict reliable lead performance with new designs with resultant patient deaths, morbidity and financial burden on the health care delivery system. It is important that a study such as this be performed for the following potential positive outcomes:

Investigate the relationship between lead stiffness and curvature evident by imaging in implanted leads which would permit the development of ISO standards. The development of these standards will lead to qualifying safer products for human implantation.

Provide manufacturers with quantifiable information across different lead designs on the effects of physical stress impacted by shoulder motion, and cardiac contraction across variable physical conditions and implanting physician techniques.

Three-D reconstruction of fluoroscopy-derived images on a background of cardiac anatomy and implant technique will provide insights into the propensity to lead failure over time.

